8.0 Study Endpoints

8.1 Describe the primary and secondary study endpoints.

Primary Outcome/Endpoint: reduction in frequency and intensity of VMS subjective hot flashes that have been recorded on a paper diary for the duration of the study.

Title: SGB CA Study

Secondary outcomes/endpoint: Changes in the following measures from baseline, 3 months, 6 months:

Objective hot flashes as measured over a 24-hour period with a validated skin conductance monitor

Memory: Mini-Mental State Exam (MMSE)

Mood: Depression Anxiety and Stress Scale (DASS) and Center for Epidemiological Studies-Depression (CES-D)

Cognition: Neurocognitive testing: California Verbal Learning Test (CVLT),List A, List B, List A Short-Delay Free Recall, List A Short-Delay Cued, Recall, List A Long Delay Free Recall, Long Delay Cued Recall, Card Rotation Tests, Digit Span (Forward and Backward), Benton Visual Retention Test,(BVRT), Finding As, Brief Test of Attention (BTA) Numbers, Brief Test of Attention (BTA) Letters, Logical Memory Subtest of Wechsler Memory Scale, Revised (WMS-R/LM-R), Letter, Semantic and Phonemic Fluency) Baseline and 3 months only.

QOL: Functional Assessment of Cancer Therapy-Breast (FACT-B McCoy Female Sexuality Questionnaire (MFSQ)),

Sleep: Pittsburg Sleep Quality Inventory (PSQI), Actigraphy changes in sleep Quality

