12.0 Withdrawal of Subjects*

12.1 Describe anticipated circumstances under which subjects will be withdrawn from the research without their consent, including stopping participation for safety reasons.

The PI can remove subjects from the research study without their approval. Possible reasons for removal include the following: if it appears to be medically harmful to the subject, or if they fail to follow directions for participating in the study, such as taking excluded medication (aspirin, anti-coagulants) prior to the SGB procedure, if it is later discovered that they did not meet the study eligibility requirements, at the discretion of the study doctor or, if the study is canceled.

12.2 Describe any procedures for orderly termination.

A subject who withdraws will be scheduled to return to the research office. At this time, written diaries will be collected and AEs will be assessed, if any. Prior to scheduling the appointment, the subject will be asked if she would like to see the PI. If yes, this will be done on the same visit. If a subject does not wish to return, she will be asked to mail or fax any written diaries. Final payment will be mailed to the subject if compensation has not already been paid out.

12.3 Describe procedures that will be followed when subjects withdraw from the research, including partial withdrawal from procedures with continued data collection.

Subjects only have the option of not participating in the cognition study. All other procedures are required as part of the study. The subject has the option to withdraw if she does not want to participate in the hot flash monitoring, actigraph monitoring and most importantly, maintaining a written diary for the duration of the study.

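### Section 12.3 gives a randomised woman who will not wear the monitor or actigraph at month 3 no stated way to keep the primary diary going

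*Combined protocol and SAP*

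**What the plan says.** Section 8.1 defines the primary endpoint as "reduction in frequency and intensity of VMS subjective hot flashes that have been recorded on a paper diary for the duration of the study". It lists monitor-measured hot flashes and actigraphy among the secondary outcomes. Section 11.1, however, counts total objective hot flashes, alongside subjective ones, among the primary outcome measures.

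The prompt heading section 12.3 asks how partial withdrawal with continued data collection will be handled. The answer allows one exception: "Subjects only have the option of not participating in the cognition study". It goes on: "All other procedures are required as part of the study". For a woman who does not want the devices the text is: "The subject has the option to withdraw if she does not want to participate in the hot flash monitoring, actigraph monitoring". The same sentence then names the diary as a further reason to withdraw.

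Two neighbouring provisions matter. Section 12.1 lets the PI remove women, among other reasons, "if they fail to follow directions for participating in the study". Section 12.2 describes a close-out visit for a woman who withdraws: "At this time, written diaries will be collected and AEs will be assessed, if any". It adds: "If a subject does not wish to return, she will be asked to mail or fax any written diaries".

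Section 11.1 plans intent-to-treat analyses of all outcomes by generalised mixed-effects models. Section 11.2 claims at least 80% power for the treatment-by-time interaction with 18 women per group.

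**The concern.** Continued collection of the diary is tied to tolerating two separate devices. The plan offers no middle course between wearing both and withdrawing, so staff who follow it have nothing else to offer a woman who is willing to keep the diary but not to wear the monitor again.

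Reasons to refuse are foreseeable. Section 13.1 lists skin reactions and inconvenience, and section 9.2 warns that a malfunction may mean another 24 hours of wear. In a 36-woman trial each avoidable loss of follow-up counts. Section 11.2 gives no post-randomisation dropout rate; it mentions withdrawals only when explaining why about 50 women are screened to randomise 36. Section 11.1 has no missing-data or sensitivity plan. If refusal were related to how a woman's symptoms go on to behave, the later diary months would be missing in a way the model could not fully correct.

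**Working it through.** **When a refusal can cost primary data.** The devices are used on three occasions (section 9.2).

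- Visit 2, baseline: randomisation takes place at Visit 3. A refusal here loses no randomised outcome.
- Visit 4, month 3: months 1 to 3 are already recorded. If the diary stops, months 4 to 6 are lost.
- Visit 5, month 6: section 11.1 computes each monthly frequency from the 30 days before the visit, so the six-month diary is complete. Only the voluntary 6-to-12-month extension could be affected.

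The exposure is therefore essentially the 3-month visit.

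**Diary months at stake.** Planned post-injection diary-months: 36 × 6 = 216. One woman leaving at month 3 loses 3, and 3/216 = 1.4%. Two women lose 6, and 6/216 = 2.8%.

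**How many women.** No refusal rate is given. Section 13.1 gives adhesive allergy 1% and itching 4%. If every affected woman declined, and the two did not overlap, 36 × (0.01 + 0.04) = 1.8 women. This is an illustration only: these are side-effect rates, and refusals for inconvenience or of the actigraph are not quantified.

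**Stated power.** The 80% in section 11.2 cannot be reproduced, because no effect size, standard deviation, within-woman correlation or number of time points accompanies it. As a stand-in I take a two-sample comparison of means, two-sided alpha 0.05, and solve for the standardised difference d that gives 80% power at 18 per group:

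d = (1.960 + 0.842) × √(2/18) = 0.934 (normal approximation); 0.961 with the t-test.

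Holding d fixed, and with n women per group contributing, power = Φ(d√(n/2) − 1.960):

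| Women contributing per group | Lost per group | Normal | t-test |
|---|---|---|---|
| 18 | 0 | 80.0% | 80.0% |
| 17 | 1 | 77.7% | 77.6% |
| 16 | 2 | 75.2% | 74.9% |
| 15 | 3 | 72.5% | 72.0% |
| 14 | 4 | 69.5% | 68.7% |

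A 5% loss (1.8 women in all, n = 18 × 0.95 = 17.1 per group) gives about 78%. The last row means 8 of 36 women, or 22%.

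Every row treats a refuser as contributing nothing. In fact she would have a baseline and three months of diary, so the rows bound the loss from above. How far the true loss falls below them depends on the within-woman correlation and on which time contrast is tested, and neither is stated.

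Section 21 gives other counts (15 and 18 by group, and thirty in total). The figures here use the 18 per group of sections 9.1 and 11.2.

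**The case against.** The strongest case against is that the gap is narrow and the text mild.

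- A reader might infer that a woman who refuses a device must leave the study. The documents do not say so. Section 12.3 speaks of an option, removal under section 12.1 is at the PI's discretion, and nothing orders the diary stopped. This stands. It is still true that the devices are compulsory and that no other course is written down.
- A reader might infer that primary data are thrown away and that the intent-to-treat plan is contradicted. Section 12.2 does the opposite for diaries already written: it retrieves them. A mixed model can use the observed months. This stands too; incomplete follow-up weakens the analysis without contradicting it.
- A reader might take 69% as the expected power. That requires 22% of women to refuse and to contribute no data, in a two-sample test that is not the stated interaction test. The documents support none of these.
- Refusal driven by lack of relief is plausible but undocumented. Lack of relief in months 1 to 3 would also be visible in the diaries already collected, which the model can partly take into account.
- Section 11.1 calls objective hot flashes a primary outcome measure, so requiring the monitor has some logic. This shows an inconsistency with section 8.1. Even if the monitor were co-primary, losing it would be no reason to lose the diary as well, and the actigraph appears only as a secondary measure.

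The protocol also shows that partial participation is workable. Section 9.2 keeps women who are ineligible for cognitive testing in the hot flash part of the study, and it lets women refuse questionnaire items.

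**Conclusion.** The point holds in a limited form. Section 12.3 makes both devices compulsory and gives withdrawal as the only stated alternative, so a randomised woman who refuses a device at month 3 has no stated way to continue the primary diary, and her months 4 to 6 may be lost. The loss is confined to those later months.

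Its effect on power is unknown and probably small: about 2 women if the listed skin reactions were the only cause and all affected women declined. The 78% to 69% range is a ceiling on the harm for losses of 1 to 4 women per group. It rests on a two-sample approximation, an effect size solved from the 80% claim, and no data from refusers. What is certain is the wording of section 12.3. The case for changing it rests on the very low cost of doing so.

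**What to change.** Rewrite section 12.3 and the matching consent text to state that a woman may stop the monitor or the actigraph, continue the diary and safety follow-up, and remain in the intent-to-treat analysis. Reserve full withdrawal for a woman who declines the diary or revokes consent. Keep the diary retrieval in section 12.2 as it is.

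Reconcile section 8.1 with section 11.1 on whether objective hot flashes are a secondary or a primary outcome, since that decides how much missing monitor data matters.

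The cost is one paragraph in the protocol, the consent wording, and one line on outcome status. The downside is that some device data may be missing for women who would otherwise have complied.

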13.0 Risks to Subjects*

13.1 List the reasonably foreseeable risks, discomforts, hazards, or inconveniences to the subjects related the subjects' participation in the research. Include as may be useful for the IRB's consideration, describe the probability, magnitude, duration, and

Title: SGB CA Study

reversibility of the risks. Consider physical, psychological, social, legal, and economic risks.

There are risks associated with participation in this study. Below is a description of the risks:

Stellate Ganglion Block with local anesthetic

Stellate ganglion injection carries the potential very rare risk of infection at the injection site, bleeding or blood clot formation at the injection site, seizures (sudden, uncontrolled muscle spasms and loss of consciousness) and nerve injury which may present as temporary paresthesia (numbness) and/or weakness. All of these rare risks are minimized with the use of fluoroscopic guidance (visualization with a type of x-ray). Other complications related to the stellate ganglion injection that can occur are puncture of the lung on the right during placement of the needle on the right neck, or an allergic reaction to the medications being injected into the subject. Temporary voice hoarseness, temporary mild shortness of breath, temporary difficulty swallowing, and temporary changes in your blood pressure may occur after the stellate ganglion injection from the numbing medicine. Possible reactions from the numbing medicine used in this study last 6-8 hours. Minor soreness at the injection site could last 1-2 days.

Tissue injection of saline (sham) below the surface of the skin

Needle placement carries the potential very rare risk of infection at the injection site, bleeding or blood clot formation at the injection site, temporary swelling of the right side of the neck from the injected liquid and an allergic reaction to the medications being injected into you. Minor soreness at the injection site could last 1-2 days.

Risk of Radiation from the x-ray

The cumulative radiation exposure from these tests is considered small and is not likely to adversely affect the subject or their disease.

The contact with radiation in this study is thought to be small. However, the effects of radiation add up over a lifetime. It is possible that having several of these X-rays may add to the subject's risk of injury or disease. When deciding to enter this study, subjects will be asked to consider past and future contact with radiation. Examples of contact with radiation include x-rays or CT scans taken for any reason or radiation therapy for cancer treatment.

Risks from the hot flash monitor

The hot flash monitor does not involve significant risk. Wearing the monitor can be a minor inconvenience. The monitor poses no risk of electric shock. Potential side effects of the monitor include (1) allergy to the paper or adhesive on the disposable electrodes (minor, 1%), (2) itching at the site of electrode attachment (minor, 4%) and (3) discoloration of the skin from the electrode gel.

Title: SGB CA Study

Risks with the Actigraph watch

The Actigraph watch does not involve significant risk. Wearing the watch can be a minor inconvenience, and the band may cause slight irritation.

Questionnaires

Being in this study may make the subject feel emotionally uncomfortable. They might feel anxious, or experience emotional reactions to some of the questions that will be asked

Cognitive Testing

Subjects may find some of the cognitive tests to be challenging, frustrating, or boring.

Confidentiality Risks

There is a risk of loss of confidentiality. Certain measures are taken to protect all personal information and data, including keeping all data sheets under lock and key and entering data into a non-network database that requires a login id and password made available only to immediate study personnel.

13.2 If applicable, indicate which procedures may have risks to the subjects that are currently unforeseeable.

Currently, there are no unforeseeable risks to the study procedures.

14.0 Potential Benefits to Subjects

14.1 Describe the potential benefits that individual subjects may experience from taking part in the research. Include as may be useful for the IRB's consideration, the probability, magnitude, and duration of the potential benefits.

Possible benefits include a reduction in the severity or frequency of hot flashes, an improvement in overall feeling of well-being and ability to perform the functions of daily living impacted by hot flashes. We do not know how long these benefits will last.

14.2 Indicate if there is no direct benefit. Do not include benefits to society or others.
Subjects who receive the sham procedure will have no direct benefit from participation.

15.0 Vulnerable Populations -N/A

16.0 Community-Based Participatory Research-N/A

Sharing of Results with Subjects

16.1 Describe whether results (study results or individual subject results, such as results of investigational diagnostic tests, genetic tests, or incidental findings) will be

Title: SGB CA Study

shared with subjects or others (e.g., the subject's primary care physicians) and if so, describe how it will be shared.

Study results will not be shared with subjects as they are considered experimental and are not required or related to their on-going medical care.

17.0 Setting

17.1 Describe the sites or locations where your research team will conduct the research.

Northwestern Medicine, formerly the Northwestern Medical Faculty Foundation, maintains a dedicated Pain Medicine Center located in the Galter Pavilion at the Northwestern University Chicago campus. The stellate ganglion blockade or sham injection will take place at this facility.

Consenting, questionnaire completion and cognition testing will take place in the research office of [name] at [name] or [name], Arkes Pavilion, Department of Anesthesia.

- Identify where your research team will identify and recruit potential subjects.***

IRB approved flyers, physician provider letters and internet notices will be utilized for the study. See "Supporting Documents" section. We expect that potential subjects will contact the research office as a result of the recruitment aids or will be referred to us by health providers.

At UIC under the supervision of [name], all computers have access to a secure server which is accessed through a unique IT department provided log-in. All electronic data are stored on the secure server. Only delegated logins have the ability to view or edit the information stored in on this server. Currently two of the 10 computers are equipped with a Biolog Transfer box, Biolog DPS software (for downloading and convert Biolog data) and Biolog 3.7, the most recent version of the software used to score and edit the Biolog data. Eight computers are currently equipped with the Actiware software (version 5.7) which is used to configure, download and score Actiwatch data. The downloading platform can be moved between computers as needed.

- *Justify the feasibility of recruiting the required number of suitable subjects within the agreed recruitment period. For example, how many potential subjects do you have access to? What percentage of those potential subjects do you need to recruit?*

Based on our experience with previous studies, we estimate we would need to screen 50 women to randomized 36 women. This is a small sample size. We do not anticipate problems in obtaining a complete sample size over the next year.

- *Describe the time that you will devote to conducting and completing the research. (Note: This description is intended to provide the IRB with information relative to conduct of the study as relevant for the protection of research subjects, not for effort reporting.)*

We anticipate that the study team will contribute 2.5 days per week to the project.

- *Describe your facilities. (Note: This description is intended to provide the IRB with information relative to conduct of the study as relevant for the protection of research subjects, not for Facilities and Administration considerations.)*
Already addressed in Section 17.0 and 18.0.

- *Describe the availability of medical or psychological resources that subjects might need as a result of an anticipated consequences of the human research.*

- *Describe your process to ensure that all persons assisting with the research are adequately informed about the protocol, the research procedures, and their duties and functions.*

Title: SGB CA Study

Prior to the inception of the study and after IRB approval has been obtained, the research team will meet to review the protocol. Safety endpoints will be reviewed and study logistics will be coordinated and agreed upon.

19.0 Prior Approvals

19.1 *Describe any approvals that will be obtained prior to commencing the research.*

We will obtain radiation safety by means of the Radiation Dosimetry Form.

20.0 Recruitment Methods

20.1 *Describe when, where, and how potential subjects will be recruited.*

IRB approved flyers, physician provider letters and internet notices will be utilized for the study. See "Supporting Documents" section. We expect that potential subjects will contact the research office as a result of the recruitment aids or will be referred to us by health providers. Subjects will be asked to come to the research office for consenting if they are interested in the study.

20.2 *Describe the source of subjects.*

We expect that the majority of subjects will come from the practices of Northwestern Medicine providers.

20.3 *Describe the methods that will be used to identify potential subjects.*

IRB approved flyers, physician provider letters and internet notices will be utilized for the study. See "Supporting Documents" section.

20.4 *Describe materials that will be used to recruit subjects. (Attach copies of these documents with the eIRB+ application. For advertisements, attach the final copy of printed advertisements. When advertisements are taped for broadcast, attach the final audio/video file. You may submit the wording of the advertisement prior to taping to preclude re-taping because of inappropriate wording, provided the IRB reviews the final audio/video file.)*

See "Supporting Documents" section.

20.5 *Describe the amount, timing, and method of any payments to subjects. (E.g., Gift card, Clinker, check.)*

The study will pay for parking in the hospital parking lot located on St. Clair St., between Superior and Huron Streets. Their parking ticket will be validated by the research staff and paid for up to six hours.

Subjects who agree to take part in this research study, will be paid \$200.00 by check at study completion for time and effort. If they agree to collect hot flash data for an additional six months after completion of the study, they will be paid an additional \$100.00 if they complete a written diary for each of the six months. They may choose to have the final check mailed to them, or they may come to the clinic to retrieve their check if that is more convenient.

Title: SGB CA Study

21.0 Local Number of Subjects

21.1 *Indicate the total number of subjects to be accrued locally* 36

21.2 *If applicable, include a break-down of subjects by study location or procedure group* 15 women will be in the SGB procedure group and 18 women will be in the sham group. All women will be recruited and followed at Northwestern.

21.3 *If applicable, distinguish between the number of subjects who are expected to be enrolled and screened, and the number of subjects needed to complete the research procedures (i.e., numbers of subjects excluding screen failures.)*

Thirty enrolled subjects are required to complete the study. We estimate that we would need to screen approximately sixty women to randomize thirty women.

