9.0 Procedures Involved

9.1 Describe and explain the study design.

Title: SGB CA Study

We aim to conduct a randomized, single-site, sham-control clinical trial of SGB on VMS in 36 women with breast cancer on anti-estrogen therapy (18 per group). We will need to screen and enroll approximately 50 women to randomize 36 women. Some women may not qualify due to insufficient number of hot flashes or there may be some withdrawals. The primary entry criterion will be 28 or more moderate to very severe hot flashes per week. VMS will be measured by self-report on a written daily dairy over a 6-month period. Secondary outcomes include changes in mood, sleep, quality of life, memory performance with neurocognitive testing, and objective hot flashes measured by ambulatory monitoring (skin-conductance temperature monitoring) for 24 hours at baseline, three months and six months.

Randomization and Masking Procedures A computer-generated 1:1 block randomization scheme will be used to assign participants to receive either a SGB with bupivacaine or a sham injection with saline. Randomization will be performed by the injectionist immediately before the injection procedure by opening an opaque envelope to reveal the participant number and group assignment printed on an index card. Randomization assignment will be kept under lock and key. Participants and all other study personnel, including those who will perform follow-up evaluations, will be blinded to group assignment. The injectionist will not have access to the written VMS diaries until the conclusion of the study.

9.2 Provide a description of all research procedures being performed and when they are performed, including procedures being performed to monitor subjects for safety or minimize risks.

Screening Visit 1

Recording of Hot Flashes

After the participant has reviewed and signed the consent form, they will be interviewed to determine if they are a candidate for the study. We will ask them to provide information about themselves and their medical history. A member of the study team will administer the Depression Anxiety and Stress Scale (DASS) to ensure that participants are not suffering from extreme anxiety or depression. If they are found to have any of these conditions and meet the exclusion criterion, they will not qualify for our study and will be referred to a mental health provider.

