Assignment to groups will be done by randomization similar to flipping a coin. They will have a 50% chance of going into either of the two groups. The study will be single blinded. Participants will not know which group they are in and only [name] will know whether they have received the stellate ganglion injection with numbing medication or the sham injection with saline. Since it is unknown how long the effects of the injection on hot flashes lasts, participants will have the option of receiving a second injection after the three month procedures if they notice an increase in the severity or frequency of their hot flashes. They will receive the same injection (bupivacaine or sham) that they got at the beginning of the study.

Before the procedure, a medication line will be inserted into a vein in the arm. An oxygen monitor and blood pressure cuff will also be placed. They will be positioned on their back for this procedure. Their neck will be swabbed with disinfectant to clean the skin, and sterile equipment and technique will be used for the entire of the procedure. With the use of a low dose x-ray machine (fluoroscopy machine) to help guide the injection, a bone in the right side of the neck (C6) will be identified and local anesthesia or numbing medicine (1% lidocaine) will be injected to the skin overlying the bone.

Title: SGB CA Study

For subjects receiving the stellate ganglion injection, a small needle will be placed through the numbed skin on the front of the right side of the neck to make contact with the tissues over the C6 (neck) bone. The correct position of this needle will be confirmed by injecting a small amount of dye that can be seen by [name] under x-ray. Then 10 cc or about 2 teaspoons of 0.5% bupivacaine (numbing medicine) will be injected and the needle will be removed.

In participants put in the sham injection group, the needle will be placed in the superficial tissues overlying the front right neck (C6 bone), just underneath the skin. 5 cc of saline fluid will be injected and the needle will be removed. This procedure will take a few minutes. After it is completed, they will stay in the office for about half an hour for observation. Their blood pressure will be checked.

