Data will be analyzed using the PROC MIXED, PROC GLIMMIX and PROC NLMIXED in SAS statistical software version 9.2. For the correlation between changes in objective VMS and changes in memory performance, we propose to examine the correlation between frequency of total objective VMS and verbal learning by conducting Pearson correlations to examine associations between changes in cognitive performance and changes in VMS. We will conduct partial correlations to examine whether these associations remained significant after controlling for changes in sleep quality (PSQI and actigraphy-based measures).

11.2 Provide a power analysis, if necessary.

A sample size of 18 in each treatment group will provide at least 80% power to test the two-way interaction between Treatment and Time with a significance level set at 0.05.

Title: SGB CA Study

We will need to screen and enroll approximately 50 women to randomize 36 women. Some women may not qualify due to insufficient number of hot flashes or there may be some withdrawals.

11.3 Describe the steps that will be taken to secure the data to maintain confidentiality (e.g., training, authorization of access, password protection, encryption, physical controls, certificates of confidentiality, and separation of identifiers and data) during storage, use, and transmission

Research files and case report forms will be stored in the research offices of [name] and will be kept in locked offices with access only to the research team. Wherever possible, subject data will be stored using only the study ID. Measures will be taken to protect all personal information and data, including keeping all data sheets under lock and key and entering data into a database that requires login identification and a password made available only to immediate study personnel. The entire study team has taken the CITI training and is familiar with confidentiality requirements and procedures.

Downloaded data from the Biolog hot flash monitor and the actigraph watch will be processed, stored, and analyzed in password-protected network at the University of Illinois in Chicago of [name]. Data related to cognitive assessments will be stored and analyzed at the University of Illinois at Chicago in [name] lab.

11.4 Describe any procedures that will be used for quality control of collected data

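### Section 21 gives two further sample sizes (15 + 18 = 33, and 30 randomised from about 60 screened) that contradict the 36 randomised, 18 per group, used in the rest of the plan

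*Combined protocol and SAP*

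**What the plan says.** The study design (section 9.1) describes a trial "in 36 women with breast cancer on anti-estrogen therapy (18 per group"), drawn from about 50 women screened and enrolled. On allocation it says "A computer-generated 1:1 block randomization scheme will be used to assign participants", and section 11.4 repeats this. The description of Visit 3 in section 9.2 says of participants: "They will have a 50% chance of going into either of the two groups".

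The power section (11.2) says "A sample size of 18 in each treatment group will provide at least 80% power to test the two-way interaction between Treatment and Time", at a significance level of 0.05, and repeats the figure of about 50 women for 36 randomised. The answer on recruitment feasibility (before section 19.0) also gives 50 screened for 36 randomised.

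Section 21.0 gives three different numbers in consecutive items:

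- 21.1: "Indicate the total number of subjects to be accrued locally* 36".
- 21.2: "15 women will be in the SGB procedure group and 18 women will be in the sham group".
- 21.3: "Thirty enrolled subjects are required to complete the study", followed by "We estimate that we would need to screen approximately sixty women to randomize thirty women".

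**The concern.** A protocol should give one number to randomise and one split between the arms. This one gives three totals. It states two splits (18/18 and 15/18), and 1:1 allocation of the thirty in 21.3 implies a third (15/15).

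Section 21 is where an approver or coordinator would look for the local accrual limit, and the two items that break down its total disagree with that total. The number of allocation envelopes and the point at which accrual stops both depend on this figure.

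The power claim is tied to 18 per group. Without an effect size, variance or within-subject correlation in 11.2, nobody can tell whether it would survive at 33 or 30.

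The screening figures also imply different workloads for the twelve-month enrolment period in section 7.2.

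**Working it through.** **Totals and split**

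| Source | Randomised or accrued | Split | Screened |
|---|---|---|---|
| 9.1 | 36 | 18/18, 1:1 | about 50 |
| 11.2 | 36 | 18/18 | about 50 |
| Feasibility answer | 36 | not given | 50 |
| 21.1 | 36 | not given | not given |
| 21.2 | 15 + 18 = 33 | 15/18 (0.83:1) | not given |
| 21.3 | 30 | not given | about 60 |

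36 − 33 = 3 women (3/36 = 8.3%). 36 − 30 = 6 women (6/36 = 16.7%). A total of 33 is odd, so it cannot divide equally between two arms.

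**Could 30 mean completers?** The first sentence of 21.3, taken alone, could mean 30 completers out of 36 randomised. The second sentence makes 30 the number randomised, so that reading fails.

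**Screening yield**

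- 9.1, 11.2 and the feasibility answer: 36/50 = 72%.
- 21.3: 30/60 = 50%.
- Screening needed for 36 randomised: 36/0.72 = 50, or 36/0.50 = 72. The difference is 22 women.
- Over twelve months: 50/12 = 4.2 per month, or 72/12 = 6.0 per month.

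**The plan's power figure.** It cannot be reproduced. Section 11.2 gives no effect size, standard deviation, within-subject correlation or dropout rate. The 52% and 4% decreases quoted from the earlier trial in section 2.2 come without a standard deviation and are not named as the design effect.

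**Precision.** The standard error of a between-group difference, relative to 18/18, is √[(1/n₁ + 1/n₂)/(2/18)]:

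- 15/18: √(0.12222/0.11111) = √1.1 = 1.049, so 4.9% larger.
- 15/15: √(0.13333/0.11111) = √1.2 = 1.095, so 9.5% larger.

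**Conditional power.** This assumes a two-sample t-test at two-sided 0.05, standing in for the Treatment-by-Time test. The standardised difference d is solved from an assumed power at 18/18.

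For exactly 80% at 18/18, the normal approximation gives d = (1.960 + 0.842) × √(2/18) = 0.934, and the noncentral t gives d = 0.961. The table uses the noncentral t.

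| Assumed power at 18/18 | Power at 15/18 | Power at 15/15 |
|---|---|---|
| 80% | 75.9% | 72.0% |
| 90% | 86.9% | 83.7% |

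The normal approximation for the first row gives 76.2% and 72.5%. To keep 80% power, 18/18 must itself give at least 83.8% (for 15/18) or 87.0% (for 15/15).

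**The case against.** The strongest reply is that the working design is not really in doubt. The total of 36 appears in the design, power and feasibility text and in 21.1, the very item that asks for total accrual. Both descriptions of randomisation are 1:1. The outliers are two answers on an institutional form, probably a slip or text left from another design, and a 1:1 block scheme would not be built as 15/18. This makes 36 the best-supported figure, but only by repetition. Reading 15 as a slip for 18 repairs 21.2 and leaves 21.3 untouched, and an accrual stop at 30 remains conceivable.

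The second reply is that no loss of power has been shown. Section 11.2 claims 80% or more, which may include reserve. The t-test is only a stand-in, the figures do not apply if the trial randomises 18/18, and section 1.1 calls the study a pilot. All of that is accepted, and the power figures are illustrative only.

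The third reply is that the screening denominators may differ. Sections 9.1 and 11.2 speak of women screened and enrolled and count withdrawals in the gap, while 21.3 speaks only of screening. This weakens the conflict, but the feasibility answer uses screening alone and still gives 50 for 36. The figure of 72 screened appears nowhere in the plan. It is 21.3's yield applied to 36.

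Finally, the missing power inputs would be a gap even if section 21 were consistent. That is correct. They matter here because their absence prevents any reader from judging the power at 33 or 30.

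**Conclusion.** The concern holds, and the text must be corrected. Sections 21.2 and 21.3 contradict 9.1, 11.2, the feasibility answer and 21.1 on the number randomised. Section 21.2 also contradicts the 1:1 allocation, and 21.3 contradicts the screening yield given elsewhere. The discrepancies are 3 and 6 women out of 36 (8% and 17%), and a yield of 50% against 72%. This conclusion needs only the plan's own numbers.

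The effect on power is conditional on an unstated effect size and on a simple two-group comparison. No stated power covers 33 or 30, but the plan does not allow the conclusion that either falls below 80%. Nor does it settle which total was intended.

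**What to change.** If 36 is intended:

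1. Change 21.2 to 18 women in the SGB group and 18 in the sham group.
2. Change 21.3 to 36 randomised. If a number of completers is wanted there, give it separately and label it as such.
3. Use one screening estimate in 9.1, 11.2, the feasibility answer and 21.3: about 50 (72% yield) or about 72 (50% yield). Say whether it counts women screened or women enrolled.
4. In 11.2, say that the 80% refers to 18 per group analysed, and give the effect size, variance and within-subject correlation used for the Treatment-by-Time test. If withdrawals after randomisation are expected, restate the power for the number expected to be analysed.

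If 33 or 30 was intended, change 9.1, 11.2, the feasibility answer and 21.1 to match, reconcile the split with the allocation ratio, and recalculate the power from stated inputs.

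At 36 these are wording changes and add no randomised patients. The stated power may come out somewhat lower once its inputs and any withdrawals are written down. If the 50% yield is the realistic one, about 22 more women must be screened.
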